Study Protocol and Statistical Analysis Plan

Title: Improvements in upper extremity function following intensive training are independent of corticospinal tract organization in children with unilateral spastic cerebral palsy: A clinical randomized trial.

NCT: 02918890

Date: 5/1/2014

Study Objectives

This study aims to test the hypothesis that improvements in upper extremity function following either constraint induced movement therapy (CIMT) or bimanual training depend on corticospinal tract (CST) laterality and type of training (unimanual vs. bimanual) in children with unilateral spastic cerebral palsy (USCP). Specifically, we predict that children with a maintained contralateral CST will respond equally to CIMT and bimanual training, while children with ipsilateral CST laterality will be less responsive to CIMT than bimanual training.

Study Design

All study procedures will be approved by the Institutional Review Boards of Teachers College, Columbia University, where the treatments will be conducted, the Burke Medical Research Institute, where TMS evaluations will be performed, and Weill Cornell Medicine, where magnetic resonance imaging (MRI) will be performed.

We will recruit participants from clinics in the NYC area, our website (<http://www.tc.edu/centers/cit/>), ClinicalTrials.gov (NCT02918890), and online support groups. We will obtain written informed consent and assent from children and their caregivers.

We will randomize participants to receive either 90 hours of CIMT or Hand-Arm Bimanual Intensive Training (HABIT) after they complete all baseline outcome measures. Block randomization will be implemented for each cohort of participants, with each cohort stratified by age, sex, baseline hand function and CST connectivity pattern as closely as possible. Randomization will occur offsite using concealed allocation to receive either CIMT or HABIT. Intervention will be delivered in a day-camp model for 6 hours/day over 15 days for a total of 90 hours.

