The inclusion criteria will be: 1) ages 6 to 17 years, 2) diagnosed with USCP 3) capable of participating in a 15 day, 6 hours/day day camp while separated from caregiver(s), 4) capable of following directions regarding hand use and testing, 5) capable of communicating needs, 6) mainstreamed in age-appropriate school classroom, and 7) able to lift the more affected arm 15cm above a table surface and grasp light objects. The exclusion criteria will be: 1) unwillingness to comply with instructions or other behavioral issues making delivery of an intensive therapy infeasible, 2) health problems unassociated with hemiplegia, 3) visual impairment that could interfere with participation, 4) orthopedic surgery on the more affected hand within 1 year, 5) presence of metallic objects in the body, and 6) botulinum toxin in the more affected upper extremity within the past 6 months or intended treatment within the study period, 7) seizures after the age of 2 years, 8) family history of seizure disorders, 9) current medication use to lower the seizure threshold, 10) claustrophobia, or 11) pregnancy.

We aim to recruit 82 participants based on sample size calculations from results of the Assisting Hand Assessment (AHA) and Jebsen-Taylor Test of Hand Function (JTTHF) outcomes of a prior CIMT/HABIT randomized controlled trial and pilot data.

Methodology

Children will participate in an intensive hand training intervention using either one (CIMT) or both (HABIT) hands. During the intervention, children will be paired with a trained interventionist, with an interventionist:child ratio of at least 1:1. We will recruit and train physical and occupational therapists, graduate students in kinesiology/neuroscience, speech pathology, and psychology, and undergraduates to be interventionists. Interventionists will be supervised by experienced PT/Ots. Both the interventionists and supervisors will be blinded to CST connectivity patterns. Prior to the intervention, a training session will be conducted by the supervisors for standardization based on the established manual of procedures for CIMT and HABIT. Fidelity will be reinforced by supervisors during the day camp and daily post-camp meetings. Participants receiving CIMT and HABIT will be located in separate rooms, with each room being supervised by experienced PTs/OTs who will model and ensure uniformity of treatment. Each day, interventionists will attend team meetings to discuss the progress and needs of each child.

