Participants will work one-on-one with their interventionist or in groups, and activities will be divided into whole and part task practice. Whole task practice involves sequencing successive movements within the context of activities (e.g., games, arts and crafts, goal training). The activities will be performed continuously for at least 15 to 20 minutes. Targeted movements and spatial and temporal coordination will be practiced within the context of completing the task. Part task practice will involve breaking down motor skills into smaller components and reinforcement of successive approximations of the desired behavior (e.g., card turning to promote forearm supination) while increasing repetitions and progressing skill requirements. This approach will also serve to increase treatment intensity by requiring as many repetitions as possible over repeated 30 second intervals (typically a minimum of 5 intervals).

Constraint-Induced Movement Therapy

CIMT will be modified to be child-focused, using a cotton sling fastened to the child's trunk with the distal end enclosed to prevent using the less affected arm or hand as an assist. The sling will be continuously worn throughout the intervention, and breaks of up to 30 minutes will be given as requested. To engage the child in the intervention and to maintain engagement, we will establish a list of fine motor and manipulative gross motor activities that elicit movement behaviors of interest that include a battery of age-appropriate, unimanual functional and play activities. Interventionists will select tasks based on which train the targeted hand impairments and the child's interest. Task difficulty will be progressed as children improved by requiring greater speed, accuracy, or movement repetition.

Hand-Arm Bimanual Intensive Therapy

We will establish a list of age-appropriate fine and gross motor activities that require use of both hands. Activities will be chosen by taking into consideration the role of the more affected upper extremity (UE) increasing in complexity from passive assist to active manipulator. Children will be asked to use the more affected UE in the same manner as that of the non-dominant limb of a typically developing child. Directions will be provided

to the child before the start of each task to avoid use of compensatory strategies, specifying how each hand will be used during the activity.

Outcome Measures

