participant will be screened for movement artifact, and slices showing artifact will be removed. Since images are obtained using 65 gradients, up to 30% of slices may be removed without compromising feasibility of tract reconstruction. Using DTI Studio, we will place region of interest seeds in the affected motor cortex and cerebral peduncle, and later in the unaffected motor cortex and cerebral peduncle. We will use tractography to find tracts that pass through both regions of interest. We will categorize each CST as present or absent. If there is a present CST on the affected side, the child will be categorized as having a contralateral CST. If there is not a CST present on the affected side, and a CST present on the other side, the child will be categorized as having an ipsilateral CST.

Statistical Analysis Plan

This will be an intention-to-treat study. If a child misses their 6 month follow-up assessment, we will impute their missing data based on the average change data for other participants in their subgroup. Statistical analyses will be performed using SPSS (IBM). A treatment (CIMT, HABIT) x CST connectivity pattern (contralateral, ipsilateral, bilateral) x test session (pre-, post-, 6 month) ANOVA with repeated measures on test session will be performed on all measures and Newman-Keuls post hoc tests will be performed where appropriate. Regression analyses will be done to determine predictors of outcomes. For children with a bilateral CST, correlations will be done between the LI and changes in outcome measures. Statistical significance will be considered at the $p<0.05$ level.

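### Arm and room coincide in every camp cohort, and the ANOVA has no cohort or room term: the overall CIMT–HABIT comparison may look too precise, while the CST interaction test is largely spared

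*Combined protocol and SAP*

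**What the plan says.** Under Study Design, allocation is by child within camp cohort: "Block randomization will be implemented for each cohort of participants". Each cohort is also stratified, as closely as possible, by age, sex, baseline hand function and CST pattern. Neither the number nor the size of the cohorts is given.

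Under Methodology, delivery is by arm: "Participants receiving CIMT and HABIT will be located in separate rooms, with each room being supervised by experienced PTs/OTs". Staff backgrounds vary widely: "We will recruit and train physical and occupational therapists, graduate students in kinesiology/neuroscience, speech pathology, and psychology, and undergraduates to be interventionists". The ratio of interventionists to children is at least 1:1, with a manual, supervisor-led training and daily meetings. Some activity is shared: "Participants will work one-on-one with their interventionist or in groups". How supervisors and interventionists are assigned to the two rooms, and whether they change rooms between cohorts, is not stated.

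The Statistical Analysis Plan section specifies a treatment × CST pattern × session model: "ANOVA with repeated measures on test session will be performed on all measures". It has no cohort, room or staff term. The target of 82 children is attributed to "outcomes of a prior CIMT/HABIT randomized controlled trial and pilot data", with no mention of a design effect.

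**The concern.** Although children are randomized one by one, in each cohort all CIMT children share one room and all HABIT children another. A strong supervisor, a more experienced staff mix or a lively group would move the gains of everyone in that room together. Such an effect enters the CIMT–HABIT difference directly, yet the ANOVA judges that difference against child-to-child variation, as if each child were an independent observation.

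Two things are at stake. The first is precision: an overall arm difference could be declared significant too readily. The second is bias: if the same staff always led the same arm, the comparison would be partly of staff, and neither more children nor more cohorts would remove that. The predictions under Study Objectives concern the interaction with CST pattern and the CIMT–HABIT contrasts within patterns, so it matters which of the planned tests are exposed.

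**Working it through.** **The plan's own figure.** The target of 82 cannot be reproduced, because effect size, SD, power and dropout are not given. Assuming 1:1 allocation, two-sided 5% and independent children, 41 per arm corresponds to d = 0.62 at 80% power: 2 × (1.96 + 0.84)² / 0.62² ≈ 41.

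**Inputs.** From the documents: 82 children, blocks within cohort, one room per arm, 5% level. Assumed: 1:1 allocation; 4 to 8 cohorts; ICC of the gain within a room of 0.02, 0.05 or 0.10. Children per room: m = 41/4 = 10.25 or 41/8 = 5.125.

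**Overall CIMT–HABIT comparison, no cohort variance.** Design effect DE = 1 + (m − 1) × ICC. The standard error is understated by a factor √DE. The actual level of a nominal 5% test is 2 × [1 − Φ(1.96/√DE)].

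| ICC | 4 cohorts: DE, √DE, level | 8 cohorts: DE, √DE, level | Simulated level, 8 to 4 cohorts |
|---|---|---|---|
| 0.02 | 1.19, 1.09, 7.2% | 1.08, 1.04, 6.0% | about 5–7% |
| 0.05 | 1.46, 1.21, 10.5% | 1.21, 1.10, 7.4% | about 6–11% |
| 0.10 | 1.93, 1.39, 15.8% | 1.41, 1.19, 9.9% | about 9–17% |

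For example, with 4 cohorts and ICC 0.05: 1 + 9.25 × 0.05 = 1.46, and √1.46 = 1.21. At that ICC the 82 children carry the information of 82/1.46 ≈ 56 (4 cohorts) or 82/1.21 ≈ 68 (8 cohorts) independent children.

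**Offset from the omitted cohort term.** Let the total variance of the gain be 1, with v_r from rooms and v_c from cohorts, and let k be the number of cohorts. The ratio of true to reported variance of the arm difference is about

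[m·v_r + (1 − v_r − v_c)] / [(1 − v_r − v_c) + (v_r + v_c)(1 − 1/k)].

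Roughly, the standard error is too small only when (m − 1)·v_r exceeds v_c.
- v_r = 0.01, v_c = 0.10: with 4 cohorts 0.9925/0.9725 = 1.02, simulated level 5.2%; with 8 cohorts 0.941/0.986 = 0.95, simulated level 4.5%.
- v_r = 0.02, v_c = 0.10: simulated level about 4.4–5.8%.
- v_r = 0.05, v_c = 0.05, 4 cohorts: 1.4125/0.975 = 1.45, simulated level 9.9%.

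So a weak room effect can be hidden by cohort variance, and a moderate one with few cohorts is not.

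**CIMT–HABIT within one CST pattern.** Fewer children per room belong to a single pattern, so the design effect shrinks. If 25% are ipsilateral (an assumption) and ICC is 0.10:
- 4 cohorts: 10.25 × 0.25 = 2.56 per room, DE = 1 + 1.56 × 0.10 = 1.16, level 6.8%.
- 8 cohorts: 5.125 × 0.25 = 1.28 per room, DE = 1 + 0.28 × 0.10 = 1.03, level 5.3%.

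Simulations over the assumed ranges gave about 5–8%.

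**Treatment × CST × session.** Because cohorts are stratified by CST pattern, each room is meant to mix patterns. A room effect that adds the same amount to every child then cancels in the contrast between patterns. Simulated level: 4.0–5.0% in one set of runs (no cohort variance) and about 5% throughout in another. A room effect that differed by CST pattern would not cancel.

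**The case against.** The strongest case against has five parts.

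1. **The central hypothesis is an interaction, and that test holds its level.** This stands. A reader might infer that the main test of the trial is invalid; the design does not support that, because rooms mix CST patterns. The larger figures belong to the overall arm comparison.

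2. **The direction of the error is not certain.** This stands in part. Besides cohort variance, age, sex and baseline hand function are balanced by design but left out of the model, which makes the error term too large. If they were perfectly balanced within cohort and explained 20% of the variance in gain, a simulation put the level at 3.7–5.0% for ICC 0.02, 4.5–8.4% for 0.05 and 6.9–13.2% for 0.10. Inflation survives at the higher ICCs.

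3. **Fixed staff per arm is an inference.** This stands. A reader might take separately supervised rooms to mean that each arm keeps its own supervisors throughout. The documents neither say so nor rule it out, so the bias is a possibility left open by the plan, not an established flaw.

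4. **Delivery is individualized and standardized.** Pairing at 1:1 or better, tasks chosen for each child, the manual, fidelity supervision and off-site blinded AHA scoring all argue for a low ICC. They reduce the room effect but cannot show it to be zero.

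5. **A room-level model is weak with few cohorts.** With 4 to 8 cohorts the room variance has only about 3 to 7 degrees of freedom, and its estimate was zero or negative in 39–51% of simulated runs at ICC 0.02 to 0.05. An approximation to the random-room model nevertheless held 3–6%, and a cohort-level paired comparison held about 4–6%. The power cost is real. At d = 0.62, ICC 0.05 and 4 cohorts, the rejection rate falls from about 77% (at an inflated level) to about 41%. The paired comparison has 37% power with 4 cohorts and 60% with 8. That makes such a model debatable as the only primary test.

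**Conclusion.** The concern holds in a limited form. Within each cohort, room and staff effects cannot be separated from treatment, and the ANOVA omits both the cohort block used in randomization and any room term. Under the assumed 4 to 8 cohorts and room ICCs of 0.02 to 0.10, the nominal 5% level of the overall treatment × session comparison becomes roughly 5–17%, provided omitted cohort variance and stratifiers do not offset the room correlation. Contrasts within one CST pattern are only mildly affected (about 5–8%), and the three-way test is essentially unaffected by an additive room effect. Cohort count and ICC are assumptions throughout, so the size is a range and not an estimate. If supervisors or interventionists do stay with one arm, the arm difference is also biased, and that can be prevented only in the conduct of the camps.

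**What to change.** 1. **Model.** Add cohort (cohort × session) to the planned model as a blocking factor, since randomization is blocked on it. This step is not enough for the arm comparison: it takes cohort variance out of the error and so removes the offset shown above. With v_r = 0.01, v_c = 0.10 and 4 cohorts, the variance ratio goes from 1.02 to about 0.9925/0.90 = 1.10.

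2. **Arm comparisons.** For CIMT–HABIT comparisons, overall and within CST pattern, also report a mixed model with a random cohort-by-arm (room) effect and small-sample degrees of freedom, or a cohort-level paired comparison. Report the estimated ICC, and base any claim of an overall arm difference on this analysis. State the number of cohorts.

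3. **Conduct.** In each cohort allocate interventionists to the two rooms at random within profession, and rotate supervisors between the CIMT and HABIT rooms from cohort to cohort. Record who worked where.

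The cost is SAP wording and a staffing rota, with no added children or staff. The downside is a clearly wider interval and lower power for the overall arm comparison when cohorts are few. The interaction test keeps nearly all its degrees of freedom.

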We will use several measures of hand function to capture different aspects of manual ability. All measures will be administered immediately before treatment (pre-test), within two days after (post-test), and 6 months after treatment (follow-up). Assessments will be administered by an experienced physical or occupational therapist who is blinded to the treatment allocation and CST connectivity of each child.

The primary outcome measures will be the Assisting Hand Assessment (AHA) and Jebsen-Taylor Test of Hand Function (JTTHF). The AHA will measure bimanual hand use, while the JTTHF will measure unimanual dexterity of the affected hand.

AHA: The AHA is a validated test for measuring bimanual hand use in children with UE impairments. The AHA measures the use of the more affected hand in bimanual activities during a play-like testing session. Sessions will be videotaped and scored off-site by a blinded evaluator. The AHA has excellent validity, reliability (0.97-0.99) and responsiveness to change. The AHA units will be used for the analysis. The smallest detectable difference (SDD) for AHA is an improvement of at least 5 units.

JTTHF: The JTTHF measures the time taken to complete six unimanual tasks, which include flipping cards, moving small objects, and lifting cans. The total score is the amount of time taken to complete all tasks. The test will be performed on both the more affected and less affected hands. The JTTHF is well-validated and has excellent reliability.

Several secondary outcome measures will also be used. The Box and Blocks Test (BBT) will measure unimanual dexterity. The Canadian Occupational Performance Measure (COPM) will measure caregiver perceptions of a child's performance of functional goals, and satisfaction with how well the child can perform the goal. The ABILHAND-Kids is a parent-report of child's manual ability. The Pediatric Evaluation of Disability Inventory (PEDI) will be used to measure functioning in the home environment.

BBT: The BBT measures how many blocks (2.5 cm³) an individual can move from one box, over a barrier, to an adjacent box in one minute. Both hands will be tested. The BBT is valid and reliable for children with CP.

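### Intention-to-treat is declared, but no rule covers a missing or late post-test, and a complete-case repeated-measures ANOVA would drop children without one

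*Combined protocol and SAP*

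**What the plan says.** The Statistical Analysis Plan opens with the principle: "This will be an intention-to-treat study". It does not define the analysis set further. Its only rule for missing outcomes follows: "If a child misses their 6 month follow-up assessment, we will impute their missing data". The method is single imputation, with the filled-in value "based on the average change data for other participants in their subgroup". The main analysis has three factors: treatment, CST connectivity pattern and test session (pre, post, 6 month). It is described as an "ANOVA with repeated measures on test session will be performed on all measures". SPSS is named as the software, but no procedure within it.

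The Outcome Measures section sets the schedule: "All measures will be administered immediately before treatment (pre-test), within two days after (post-test), and 6 months after treatment (follow-up"). It has no rule for an assessment that is late or missed, and it does not say whether a child who leaves camp early is still tested. Under Study Design, children are randomised "after they complete all baseline outcome measures", so every randomised child should have a pre-test.

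**The concern.** The plan deals with a gap at month 6 but not with the same gap at the post-test. A conventional repeated-measures ANOVA needs all three scores. Without a post-test, a child is removed even if seen at pre-test and at 6 months, and even if a 6-month value has been imputed. That child was randomised and has baseline data, so the removal contradicts the stated principle.

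The schedule adds to the difficulty. For a child who leaves on, say, day 4, a post-test timed from the end of treatment could mean two days after leaving or two days after the cohort finishes. With no rule, staff would decide case by case, after allocation, whether and when to test such a child and whether to use a late score.

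Two things are at stake. One is precision, because observed visits are discarded. The other is the fairness of the arm comparison, if children without a post-test differ in response from those with one. The Study Objectives put the key contrast inside the ipsilateral subgroup, where each arm will hold few children and one or two losses count.

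**Working it through.** **1. What the plan provides for each event**

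| Event | Provision |
|---|---|
| Pre-test missing | Should not arise: allocation follows baseline testing (Study Design) |
| Child stops camp early | No statement on testing |
| Post-test late | Two-day target; no rule on using or excluding a late score |
| Post-test missing | None |
| 6-month visit missing | Imputed from subgroup average change |

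**2. What the stated model does with a missing post-test**

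The standard repeated-measures ANOVA takes one record per child with all three scores. The plan's own imputation at month 6 points to that form, since a model fitted to all observed sessions would not need it to keep the child. I checked the consequence on a constructed dataset of 82 children with 8 post-tests removed:

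- Complete cases: 82 − 8 = 74 children, 74 × 3 = 222 scores.
- Mixed model on observed sessions: 82 children, 82 × 3 − 8 = 238 scores.
- Difference: 16 observed scores (8 pre-test, 8 at 6 months). If some of these children also missed month 6, fewer observed scores are lost.

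**3. Precision**

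The planned 82 cannot be reproduced, because the plan gives no effect size, SD, power or dropout allowance. As an illustration I assume 41 per arm, a simple two-group comparison of means, two-sided 0.05 and 80% power. The implied standardised effect is

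d = (1.960 + 0.842) × √(2/41) = 0.62.

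If a fraction m of post-tests is missing and those children are dropped, power ≈ Φ(2.802 × √(1 − m) − 1.960).

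| m (assumed) | Children analysed, 82(1 − m) | Per cell if six equal cells | Power |
|---|---|---|---|
| 0 | 82 | 13.7 | 80% |
| 5% | 77.9 | 13.0 | 78.0% |
| 10% | 73.8 | 12.3 | 75.7% |
| 20% | 65.6 | 10.9 | 70.7% |

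This is the two-arm comparison. It is not the power for the treatment-by-CST interaction or for the ipsilateral contrast, which cannot be computed from the plan.

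**4. Bias: why its direction is unknown**

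The bias in a cell mean is (fraction dropped) × (mean change in those kept − mean change in those dropped). Assumed values, none from the documents: 14 children per ipsilateral cell (82/6 = 13.7), AHA change of 5 under CIMT and 7 under HABIT in children with a post-test, 0 in those without, and two children lost from one cell only.

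- Loss in the CIMT cell: full mean 12/14 × 5 = 4.29; full contrast 7 − 4.29 = 2.71; complete-case contrast 7 − 5 = 2.00. Understated by 0.71.
- Loss in the HABIT cell: full mean 12/14 × 7 = 6.00; full contrast 6.00 − 5 = 1.00; complete-case contrast 2.00. Overstated by 1.00.

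The sign depends entirely on which children are lost.

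**5. What a mixed model alone would recover**

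Take the CIMT case above. Assume equal SDs, a correlation of 0.6 between post-test and 6-month change, a pre-test that carries no information on change, and zero change at both visits for the two children.

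- Seen at 6 months: predicted post-test change 5 + 0.6 × (0 − 5) = 2; cell mean (12 × 5 + 2 × 2)/14 = 4.57; contrast 2.43. The model recovers 0.43 of the 0.71.
- Not seen at 6 months: nothing is recovered.

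Only obtaining the missing post-tests removes the bias in this example.

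**The case against.** A reader might infer that the plan deletes these children. It does not say so. It names SPSS but no procedure, and SPSS MIXED would keep them. Reading the model as a complete-case ANOVA is the likelier interpretation, given the wording and the imputation at month 6, but it remains an interpretation. This stands, and the point is therefore put conditionally.

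A reader might also equate stopping camp, or missing the two-day window, with having no post-test. Neither follows. The assessment schedule is not limited to children who finish camp, and no rule discards a late test. This also stands. What remains is that the plan is silent on both.

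A third inference is that children who do badly on CIMT will leave, so that the CIMT–HABIT difference is understated by some calculable amount. The documents give no stopping rate and no evidence that stopping differs by arm or CST pattern. The hypothesis concerns response, not attendance. The eligibility criteria select children able to manage a full-day camp, and the CIMT description allows breaks from the sling. Attrition may well be low.

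Finally, a mixed model is not the only remedy. Multiple imputation, or extending the imputation rule to the post-test, would also keep the child in. That is correct, but some rule is needed, and the mixed model is the simplest that uses every observed visit without filling in values.

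**Conclusion.** The concern holds in conditional form. The plan states intention-to-treat, covers only a missed 6-month visit, and leaves unstated both the testing of children who stop and the handling of a missing or late post-test. If the ANOVA is run conventionally on complete cases, a randomised child without a post-test leaves the analysis with the pre-test and any 6-month score.

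The practical size is unknown. The fall in power from 80% to about 78%, 76% or 71% rests on assumed missing rates of 5%, 10% and 20% and on a two-arm comparison back-solved from 82. The AHA contrasts in the working are invented to show that bias can run either way, and they should not be cited as estimates. The change is worth making because the stated method is worse whenever a post-test is missing and the repair is cheap.

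**What to change.** 1. **Outcome Measures.** State that every randomised child is assessed with their cohort at the scheduled end of camp and again at 6 months, whatever number of hours was completed, unless consent for testing is withdrawn. State that a late post-test is kept, with its actual date recorded.

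2. **Statistical Analysis Plan.** Replace the complete-case ANOVA with a linear mixed model (for example SPSS MIXED, session as the repeated factor, unstructured covariance) fitted to all observed sessions, with children analysed as allocated. The 6-month mean-change imputation is then not needed to keep a child in, and imputed values should not be entered as if observed.

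3. **Reporting and sensitivity.** Report hours attended and missing assessments by arm and CST pattern. Add a sensitivity analysis for outcome-dependent missingness, since the mixed model alone does not remove that bias.

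Item 1 obtains the outcomes and item 2 keeps the visits that were observed, so both are needed. The cost is revised wording, a few extra contacts to bring early leavers to a test session, and a little more analysis work in software already planned. No treatment rule changes.

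### Filling missed 6-month visits with a subgroup's average change, then analysing them as observed, can inflate the planned three-way test; how much depends on two undefined terms

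*Combined protocol and SAP*

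**What the plan says.** The Statistical Analysis Plan declares an intention-to-treat study and gives one missing-data rule, which applies only to a missed 6-month visit: "we will impute their missing data based on the average change data for other participants in their subgroup". The completed data go into "A treatment (CIMT, HABIT) x CST connectivity pattern (contralateral, ipsilateral, bilateral) x test session (pre-, post-, 6 month) ANOVA with repeated measures on test session", run on every outcome at p<0.05, and "Newman-Keuls post hoc tests will be performed where appropriate".

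The word *subgroup* is not defined. It could mean the treatment arm, the CST pattern or the treatment x CST cell. The change being averaged is not tied to the pre-test or the post-test. The plan gives no imputation-variance adjustment, sensitivity analysis or expected loss rate, and no rule for a missed post-test.

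The prediction in Study Objectives is an interaction: "children with ipsilateral CST laterality will be less responsive to CIMT than bimanual training". The recruitment target in Study Design is "We aim to recruit 82 participants".

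**The concern.** A child filled with the cell's average change sits exactly on that cell's mean. The child counts in full in the sample size and the error degrees of freedom but contributes nothing to the residual variance of that change. The F test therefore treats a mean based on fewer children as if it came from all of them, and it also underestimates the spread.

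The affected test is the planned test of the trial's stated hypothesis, on both primary outcomes. The undefined terms matter as well. One reading favours finding the hypothesised interaction, while another leaves that test near nominal but can dilute the 6-month difference. Without a definition, the choice could be made after the data are seen.

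**Working it through.** **Plan's own figure.** The target of 82 cannot be reproduced, because no effect size, SD, power or dropout rate accompanies it. It is used here only as the sample size.

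**Inputs from the documents.** 82 children; 2 arms x 3 CST patterns = 6 cells, averaging 82/6 = 13.7 children; 3 visits; alpha 0.05. The three-way test has (2-1)(3-1)(3-1) = 4 and 2 x (82-6) = 152 degrees of freedom.

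**Assumptions, not in the documents.** A fraction f of 6-month visits is missing completely at random, with f = 5%, 10%, 20% or 30% (about 4, 8, 16 or 25 children). Cells are 13-14 children, data are normal, and the correlation is 0.8 between all visits unless stated.

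**1. Cell fill, change from the visit used for the fill.** Let V be the variance of that change and n the cell size.
- True variance of the filled cell mean: V/[n(1-f)].
- Reported variance: about (1-f)V/n.
- Reported/true SE: square root of (1-f)^2 = 1-f.
- Approximate rejection rate of a single contrast: 2[1 - Φ(1.96(1-f))].

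The simulated contrast below is treatment x (ipsilateral vs contralateral), with its own error term. Simulations used 4,000 to 10,000 trials per case (Monte Carlo error about 0.2-0.7 points). Ranges cover pre-test and post-test fill and repeated runs.

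| Missing | SE ratio | Contrast, formula | Contrast, simulated | Three-way test, simulated |
|---|---|---|---|---|
| 5% | 0.95 | 6.3% | 6.2-6.6% | 5.5-6.9% |
| 10% | 0.90 | 7.8% | 7.8-8.0% | 7.2-8.6% |
| 20% | 0.80 | 11.7% | 11.6-12.3% | 10.3-11.8% |
| 30% | 0.70 | 17.0% | 18.5-18.8% | 16.3-17.9% |

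With nothing missing, the three-way test gave 4.6-5.1%. At 10% missing, every run but one gave 8.1% or less; the 8.6% came from 4,000 trials (Monte Carlo error 0.4 points). A Greenhouse-Geisser correction does not cure this: 6.9-7.2%, 9.8-11.0% and 15.8-15.9% at 10%, 20% and 30% missing. Unequal cells (17/15/9 per arm) gave 7.5-7.8% and 11.1-11.8% at 10% and 20%.

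**2. Dependence on the correlation pattern.** Take post-test fill and the pre-to-6-month change. With V(a,b) the variance of change between visits a and b:
- Reported variance x n: (1-f)V(pre,6) + fV(pre,post).
- True variance x n: V(pre,6) + V(post,6) f/(1-f).

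Under equal correlation the SE ratio is the square root of (1-f), or 0.89 at 20% missing.

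Now let post-test and 6-month scores correlate 0.95 and each correlate 0.8 with pre-test. In SD units, V(pre,6) = V(pre,post) = 2(1-0.8) = 0.4 and V(post,6) = 2(1-0.95) = 0.1. At f = 20%, reported is 0.4 and true is 0.4 + 0.1 x 0.25 = 0.425. The SE ratio is 0.97 and rejection is about 5.7% (simulated 5.5%).

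Three-way test in this case, near-equal cells, with Greenhouse-Geisser:

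| Fill from | 20% missing | 30% missing |
|---|---|---|
| Post-test | 5.6-6.4% | 6.2-7.4% |
| Pre-test | 10.4-10.5% | 14.0-15.9% |

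Uncorrected, post-test fill gave 8.3-8.9% at 20% missing, but complete data already gave 7.1-7.6%. Most of that excess is non-sphericity, not imputation.

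**3. Arm or CST fill.** The pooled mean cancels from differences between cells that share it. The true variance of a cell's own part is (1-f)^2 x V/[n(1-f)] = (1-f)V/n, which matches the reported variance. The three-way test therefore stays near nominal (simulated 4.5-5.9% at 10-30% missing). For the group that supplies the fill, the 1-f ratio of step 1 returns. At 20% missing, treatment x session rejects 8.6-9.8% under arm fill, and CST x session rejects 10.5-10.8% under CST fill.

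Cell differences also shrink. With change from pre-test, a true treatment x CST difference of 0.60 SD becomes 0.60(1-f) = 0.54, 0.48 and 0.42 at 10%, 20% and 30% missing (simulated 0.54, 0.48, 0.41). With change from post-test, only a difference arising after post-test shrinks.

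**4. Pre-to-post tests.** With their own error term they reject 4.5-5.2%. With error pooled over sessions (pre-test fill), the rates are 5.2%, 5.5% and 6.5% at 10%, 20% and 30% missing.

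**The case against.** The strongest reply is that the firm defect is two undefined terms, and that material inflation of the three-way test needs three things the documents do not state: a cell-level subgroup, an appreciable missing rate and a suitable correlation pattern. That stands as a limit on size. At 5% missing the excess is about one percentage point, and nothing in a three-week day camp with 82 children shows that 20-30% will be lost. The cell is the natural reading, because the hypothesis and the ANOVA both cross treatment with CST pattern, but it remains an inference.

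A reader might infer that the three-way test is materially inflated whichever visit is used for the fill. The documents do not support that. They give no correlations, and close tracking of 6-month scores with post-test scores is plausible when training falls between pre-test and post-test. Post-test fill then does little harm once sphericity is corrected. A reader might also infer that the whole hypothesis test is compromised. Study Objectives does not make 6 months the primary time point, and pre-to-post tests with their own error are untouched.

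The objection does not remove the problem. The plan states a deterministic fill followed by an ordinary ANOVA, and under the equal-correlation assumptions each of the three readings of *subgroup* inflates at least one planned session test. Defining the word would not be enough.

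**Conclusion.** The point holds conditionally and should be fixed before analysis. With cell-level fill, 82 children, equal correlation of 0.8 and data missing completely at random, the three-way test at nominal 5% rejects about 6%, 7-8%, 10-12% and 16-18% at 5%, 10%, 20% and 30% missing, and 6-month intervals are too narrow. With a post-test/6-month correlation of 0.95, post-test fill and Greenhouse-Geisser correction, it rejects only about 6-7% at 20-30% missing; pre-test fill still gives about 10% and 14-16%. With arm or CST fill the three-way test stays near 5%, but the matching two-way session test reaches about 9-11% at 20% missing. If change is taken from pre-test, a true 6-month interaction also shrinks by about the fraction missing. The missing rates, the correlations and the meaning of *subgroup* are assumptions, so these figures are a range and not a forecast for this trial.

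**What to change.** In the Statistical Analysis Plan, replace the mean-change fill as the main analysis with a REML mixed model for repeated measures: treatment x CST x session, unstructured covariance, Kenward-Roger or Satterthwaite degrees of freedom, on all available scores. Take the post hoc session comparisons from that model. Regressions and correlations on 6-month change should use observed values, not filled ones. The model also keeps children who miss the post-test, for whom there is now no rule.

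In simulation with Kenward-Roger, the three-way test rejected 4.6%, 4.9% and 4.3% at 10%, 20% and 30% missing. With 20% missing plus 5% missed post-tests it rejected 5.2% (673 of 13,000; Satterthwaite 5.6%).

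Multiple imputation is an alternative only if a pooling method for the 4-df three-way test is specified; it was checked here only for the single contrast (5.0%, 5.0% and 4.6%). Complete cases were also near nominal under the same missingness and equal correlation (4.6-5.2%), but they discard the earlier scores of children lost at 6 months. If the single fill is kept, label it a sensitivity analysis and define both the subgroup and the reference visit.

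The cost is SAP wording and a re-specified model, with no new data. The 6-month p-values and intervals will be less favourable than under cell fill, and the model still assumes that missingness is explained by the observed data.
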